10.1 Interim Analysis

Not applicable.

10.2 DMC analysis

Not applicable.

12 APPENDICES

12.1 Analysis Visit Windows for Safety Assessments

Table 12-1 Analysis Visit Windows Safety Assessments			
Panel A: Analysis Visit Windows for Part A			
Assessment	Visit¹	Target Study Day	Analysis Visit Window (in study days)^{2, 3, 4}
Weight, Height and BMI	Baseline	—	defined in section 9.1.1
	Part A Week 4	29	[1, 43]
	Part A Week 12	85	(43, 113]
	Part A Week 24	169	(113, 211]
	Part A Week 36	253	(211, 295]
	Part A Week 48	337	(295, 351]
	Part A Safety Follow-up	Not applicable	Use nominal visit
Vital Signs Hematology Serum Chemistry	Baseline	—	defined in section 9.1.1
	Part A Day 15	15	[1, 22]
	Part A Week 4	29	(22, 43]
	Part A Week 12	85	(43, 113]
	Part A Week 24	169	(113, 211]
	Part A Week 36	253	(211, 295]
	Part A Week 48	337	(295, 351]
Part A Safety Follow-up	Not applicable	Use nominal visit	
Standard 12-lead ECG	Baseline	—	defined in section 9.1.1
	Part A Day 15	15	[1, 22]
	Part A Week 12	85	(22, 113]
	Part A Week 24	169	(113, 253]
	Part A Week 48	337	(253, 351]
Part A Safety Follow-up	Not applicable	Use nominal visit	
Coagulation	Baseline	—	defined in section 9.1.1
	Part A Week 24	169	[1, 253]
	Part A Week 48	337	(253, 351]
Part A Safety Follow-up	Not applicable	Use nominal visit	

Table 12.1 Analysis Visit Windows Safety Assessments			
Panel B: Analysis Visit Windows for Part B			
Assessment	Visit¹	Target Study Day	Analysis Visit Window (in study days)^{2,3,4}
Vital Signs Hematology Serum Chemistry Weight, Height and BMI	Baseline	—	defined in section 9.2.1
	Part B Week 12	85	[1, 127]
	Part B Week 24	169	(127, 211]
	Part B Week 36	253	(211, 295]
	Part B Week 48	337	(295, 379]
	Part B Week 60	421	(379, 463]
	Part B Week 72	505	(463, 547]
	Part B Week 84	589	(547, 631]
	Part B Week 96	673	(631, 687] Use nominal visit
Part B Safety Follow-up	Not applicable		
Standard 12-lead ECG	Baseline	—	defined in section 9.2.1
	Part B Week 24	169	[1, 253]
	Part B Week 48	337	(253, 505]
	Part B Week 96	673	(505, 687]
	Part B Safety Follow-up	Not applicable	Use nominal visit
Coagulation	Baseline	—	defined in section 9.2.1
	Part B Week 48	337	[1, 505]
	Part B Week 96	673	(505, 687]
	Part B Safety Follow-up	Not applicable	Use nominal visit

Notes:

¹ Visit name for analysis purpose is used to report data in tables and figures.

² The analysis visit windows will be applied using the following rules for both scheduled and unscheduled visits:

1. If no numerical measurement is available within a visit window, the measurement will be considered missing for the visit.
2. If there is more than 1 numerical measurement available within a visit window, use the following rules:
 - i. The measurement closest to the target day will be used; or
 - ii. If there are multiple measurements with the same closest distance from the target day, the latest measurement will be used. For multiple measurements on the same day, unscheduled measurements will be treated as later than scheduled measurement.

³ For measurement collected on the date of first dose of study drug in Treatment Period, if it cannot be determined whether the measurement is before or after the first dose:

- a. Scheduled measurement will be treated as pre-dose observation.
- b. Unscheduled measurement will be treated as post-dose observation.

⁴ For safety Assessment, Safety Follow-up analysis visit will be based on nominal Safety Follow-up visit. If a subject doesn't have a nominal Safety Follow-up visit but has an ETT visit with study day >351 in the corresponding part, then the ETT visit will be mapped into Safety Follow-up analysis visit.

Derived Variables:

1. Age (in years) at first dose date and post-baseline visit (for listing, if applicable):
 - Obtain the age at informed consent in “yy, mm” format (e.g., 24 years, 6 months) in parent study from the Vital Signs (VS) page at the Screening Visit in parent study, and add 0.5 month to convert to days.
 - Obtain the informed consent date in parent study.

Table 12.1 Analysis Visit Windows Safety Assessments			
Panel B: Analysis Visit Windows for Part B			
Assessment	Visit¹	Target Study Day	Analysis Visit Window (in study days)^{2, 3, 4}
			
Then age (in years) at first dose = [(first dose date – informed consent date in parent study) in days + age at informed consent (in days) in parent study]/365.25.

			
2. Age (in months) at first dose date and post-baseline visit (for use in calculation of Height, BMI and weight z-scores):
 
Obtain the age at informed consent in “yy, mm” format (e.g., 24 years, 6 months) in parent study from the VS page at the Screening Visit in the parent study.
 
Obtain the informed consent date in parent study.
 
Then age (in months) at first dose or post-baseline visit = integer part of {(age at informed consent (in months) in parent study + 0.5 + diff(first dose date or post-baseline visit date, informed consent date) in months in parent study)} + 0.5.

			
3. Missing first dose date or last dose date
 
If the first dose date is missing, use Day 1 visit date.
 
If the last dose date of study drug is not available and there is no data to indicate that the subject discontinued treatment, the data cutoff date will be used instead.
 
If the subject discontinued treatment and the last dose date is missing or partial date is reported, the last dose date will be imputed based on, in descending order priority, the Early Treatment Termination (ETT) visit date, last visit date before the Safety Follow-up, or the last study drug administration date from EX SDTM domain, as appropriate. The imputation algorithm will ensure the imputed last dose date does not exceed the study participation end date.

			
4. Electrocardiogram:
 
Baseline is defined in Section 9.1.1 for Part A and 9.2.1 for Part B. If multiple ECG measurements are obtained on the same calendar day during the TE period,
 
 ○ For summary purpose, the average value will be used as the ECG on that day; ○ For threshold analysis purpose, all ECG values will be used

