**Table 3-1 Study VX19-445-115: Part A Treatment Period and Safety Follow-up Visit**

Event/Assessment a	Treatment Period Part A					Part A ETT Visit/ Departing Visit b	Part A Safety Follow-up Visit (28 ± 7 Days After Last Dose) c	Comments
	Day 1/ Returning Visit d	Day 15 (± 3 Days)	Weeks 4, 12, 24, 36 (± 5 Days)	Weeks 8, 16, 20, 28, 32, 40, 44 (± 5 Days)	Week 48 (± 5 Days) e			
Ophthalmologic examination					X	X		Subjects <18 years of age on the date of informed consent in a parent study and have completed at least 12 weeks of study drug treatment since their last ophthalmologic examination will have an ophthalmologic examination at the Part A Week 48 Visit or the Part A ETT Visit/ Departing Visit, whichever comes first. See Section 11.2.7 for acceptable assessment windows.
Complete physical examination (PE)	X				X	X		Symptom-directed PEs may be performed at any time if deemed necessary by the investigator (Section 11.2.3)
Pregnancy test	Urine		Urine	Urine	Serum	Serum	Serum	For all female subjects, at telephone contacts, a urine pregnancy test will be performed with a home kit provided by the study site. Results of the home pregnancy test will be reported to the site by telephone (Section 11.2.2).
Standard 12-lead ECG	X	X	Weeks 12, 24		X	X	X	Performed after subject has been at rest for at least 5 minutes (Sections 11.2.3, 11.2.5, and 11.2.6)
Vital signs	X	X	X		X	X	X	
Pulse oximetry	X	X	X		X	X	X	
Urinalysis	X				X	X	X	Section 11.2.2
Hematology	X	X	X		X	X	X	
Coagulation	X		Week 24		X	X	X	
Serum chemistry	X	X	X		X	X	X	
Study drug count	X	X	X		X	X		

Event/Assessment a	Treatment Period Part A					Part A ETT Visit/ Departing Visit b	Part A Safety Follow-up Visit (28 ± 7 Days After Last Dose) c	Comments
	Day 1/ Returning Visit d	Day 15 (± 3 Days)	Weeks 4, 12, 24, 36 (± 5 Days)	Weeks 8, 16, 20, 28, 32, 40, 44 (± 5 Days)	Week 48 (± 5 Days) e			
Study drug dosing	Day 1 through evening before Part A Week 48 Visit							Subjects on study drug interruption from a parent study or another qualified Vertex study may NOT begin dosing until they meet the resumption criteria in Section 9.8. The last dose of Part A should be taken on the evening before the Week 48 Visit. Refer to Section 9.6.1 for study drug administration details.

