**Summary of Changes in Ongoing CF Clinical Studies for Subjects Who Cannot Travel to the Study Site**

Protocol Change	Rationale for Change	Study Number
Addendum Version 3.0, dated 29 July 2020		

Assessments
 
Unscheduled visit(s) will be permissible at the discretion of the investigator(s) or Vertex. The unscheduled visit(s) may be conducted at any time during the study (including after the protocol defined last study visit) in the event assessments specified to be collected at a scheduled visit were not collected due to COVID-19.
	
To ensure subject safety and/or to facilitate evaluation of safety and/or efficacy if assessments are not performed per the schedule in the protocol due to COVID-19.
	
[REDACTED]
 
[REDACTED]
 
[REDACTED]
 
[REDACTED]
 
VX19-445-115
 
[REDACTED]
 
[REDACTED]

Implementaion of measures described in addenda versions 1.0 and 2.0, as applicable.
	
To ensure subject safety and/or to facilitate evaluation of safety and/or efficacy while maintaining study integrity and the safety of subjects and site personnel.
	
[REDACTED]

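### The Week 48 and Week 96 analysis windows close 14 days after target, so a later end-of-Part visit held on drug drops out of the by-visit summaries

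*SAP*

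**What the plan says.** SAP Section 12.1, Table 12-1, assigns measurements to analysis visits by study day. The Part A Week 48 window runs from after day 295 (vital signs, hematology, chemistry, weight) or after day 253 (ECG, coagulation) to day 351. The Part B Week 96 window runs from after day 631 or after day 505, for the same two groups, to day 687. The Part B cell for the first group reads, after its opening bracket, "631, 687] Use nominal visit". The last three words look displaced in the text extraction from the Part B Safety Follow-up row, whose window cell is empty. The ECG and coagulation rows give Week 96 a plain day range.

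The assignment rules are in the footnotes:
- Scope: "The analysis visit windows will be applied using the following rules for both scheduled and unscheduled visits".
- Empty window: "If no numerical measurement is available within a visit window, the measurement will be considered missing for the visit".
- Several values in a window: "The measurement closest to the target day will be used".
- Follow-up: "Safety Follow-up analysis visit will be based on nominal Safety Follow-up visit". If there is none, a subject who "has an ETT visit with study day >351 in the corresponding part" has that visit mapped to Safety Follow-up instead.

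On the protocol side, Tables 3-1 and 3-2 allow ±5 days around Week 48 and Week 96. Treatment is tied to the visit: "The last dose of Part A should be taken on the evening before the Week 48 Visit", and Table 3-2 has the equivalent entry for Week 96. COVID-19 Addendum Version 3.0, which lists this study, lets missed assessments be made up: "The unscheduled visit(s) may be conducted at any time during the study (including after the protocol defined last study visit").

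**The concern.** A nominal Week 48 visit on day 352 or later, or a nominal Week 96 visit on day 688 or later, falls outside its window. It is neither a Safety Follow-up nor an ETT visit, so footnote 4 does not pick it up. If the subject kept dosing until the evening before, the value is an on-drug measurement inside the TE Period that the by-visit tables do not use.

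Weeks 48 and 96 are the last on-treatment time points of Part A and Part B in a study whose only objective is safety. The omission falls on subjects with delayed visits. Under protocol Section 9.1.2, subjects who move to a commercial or managed-access regimen, or to another Part, within 28 days have the Week 48 or Week 96 visit in place of Safety Follow-up. They may therefore have no other end-of-treatment value.

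**Working it through.** **1. Reproduce the plan's figures.** Target day = 7 × week + 1, which gives 7 × 48 + 1 = 337 and 7 × 96 + 1 = 673. The lower bounds are midpoints between adjacent targets: (253 + 337)/2 = 295, (169 + 337)/2 = 253, (589 + 673)/2 = 631, (337 + 673)/2 = 505. The upper bounds are the midpoint between target and target + 28: (337 + 365)/2 = 351 and (673 + 701)/2 = 687.

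**2. Reach of the final windows.** The lower bound is open, so the first eligible day is the bound + 1.

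| Window | Days before target | Days after target |
|---|---|---|
| Part A Week 48, vital signs/laboratory/weight | 337 − 296 = 41 | 351 − 337 = 14 |
| Part A Week 48, ECG/coagulation | 337 − 254 = 83 | 14 |
| Part B Week 96, vital signs/laboratory/weight | 673 − 632 = 41 | 687 − 673 = 14 |
| Part B Week 96, ECG/coagulation | 673 − 506 = 167 | 14 |

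Every other window from Week 12 on reaches further past its target, from 113 − 85 = 28 days (Part A Week 12) to 505 − 337 = 168 days (Part B Week 48 ECG and coagulation). The protocol's own latest day is 337 + 5 = 342 or 673 + 5 = 678, so the final windows allow 351 − 342 = 9 days beyond it.

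**3. A late visit is on drug and in the TE Period.** If the visit is on day d and dosing continued, the last dose is on day d − 1. The TE Period runs to 28 days after that dose or to completion of participation, whichever is first. Completion cannot precede the visit, so day d is inside.

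**4. What is reported instead.** For a subject otherwise on schedule, no other scheduled value lies in the final window. Part B ECGs fall on days 169, 337 and 673 and coagulation on 337 and 673; only 673 is in (505, 687]. The preceding Part B laboratory visit, day 589, is outside (631, 687]. In Part A, day 253 (laboratory) is outside (295, 351] and day 169 (ECG, coagulation) is outside (253, 351]. The usual result is therefore a missing visit. Replacement needs another value in the window, such as an unscheduled one.

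Illustration: a Part B subject has an unscheduled ECG on day 520 and the Week 96 ECG on day 690. Day 520 is reported as Week 96, 673 − 520 = 153 days early. Day 690, only 690 − 673 = 17 days late, is not used.

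**5. Rollover subjects.** A late Week 48 value that also serves as Part B Day 1 gets no Week 48 label in Part B. Panel B has no Day 1 row, and Part B baseline is taken before the first dose of ELX/TEZ/IVA in the parent study or Part A.

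**6. How many.** The documents give no rate of late visits. Purely as an assumption, 2%, 5% or 10% of the planned maximum of about 158 would be 3.2, 7.9 or 15.8 subjects. Part B will have no more subjects than Part A.

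**The case against.** The case against giving this much weight is substantial, and most of it stands.

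- A reader might infer from the 167-day figure that Week 96 tables will commonly show values months old. That figure applies only to Part B ECG and coagulation, and step 4 shows that those tests would normally just be missing.
- A reader might infer that every make-up visit under the addendum is a lost on-drug value. For a subject who has stopped treatment, a make-up after the last visit is off drug. Where the Week 48 or Week 96 visit closed participation, it is also outside the TE Period. For a rollover subject, a make-up after the Week 48 visit falls in Part B's first window, [1, 127] for vital signs and laboratory tests. Leaving these out of Week 48 or Week 96 is reasonable.
- A reader might infer that the cap serves no purpose because Safety Follow-up is assigned by name. The windows also take unscheduled values, such as liver tests monitored after discontinuation (protocol Section 9.8.1), and some bound is needed to keep those out. The midpoint arithmetic suggests a deliberate convention.
- Late TE values still count in the laboratory, ECG and vital-sign threshold analyses (SAP 9.1.3.2 to 9.1.3.4; Section 12.1 uses all ECG values). Laboratory listings include unscheduled visits, COVID-impacted visits are listed, and nothing is tested.
- Protocol Section 9.1 expects visits within their windows, and the addendum provides in-home assessments and local laboratories so that they can be.

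The narrow gap remains: a nominal Week 48 or Week 96 visit more than 14 days late, with dosing continued, has no analysis visit.

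**Conclusion.** The gap is real but minor, and closing it is a cheap improvement. It affects only the by-visit observed-value and change-from-baseline summaries at Week 48 and Week 96. The documents do not support the inference that the overall safety assessment is compromised.

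The conclusion rests on two assumptions. First, the displaced words in the Part B row are not a nominal-visit rule for Week 96. Second, some subjects attend more than 14 days late while still dosing. COVID-delayed visits are the realistic case. Returning Part B subjects are a possible one: visit numbering resumes where they left off, and SAP 9.2.1 removes time away from the TE Period, exposure and compliance, but Table 12-1 does not say whether study day is adjusted. If it is not, an absence of more than 14 days could push an otherwise on-target Week 96 visit past day 687.

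**What to change.** In SAP Table 12-1:

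1. Set the upper bound of the Part A Week 48 and Part B Week 96 windows to the later of day 351 or 687 and one day after the subject's last dose in that Part. For rollover subjects it should be no later than the pre-dose assessment on Part B Day 1. In the illustration, the bound becomes max(687, 689 + 1) = 690, so the day-690 ECG is eligible and, at 17 days against 153, is the one used.
2. Exclude nominal Safety Follow-up measurements and ETT visits mapped to Safety Follow-up.
3. In footnote 4, make the ETT cut-off >351 for Part A and >687 for Part B. With >351 in both Parts, a Part B ETT visit on day 660 without a Safety Follow-up visit would be mapped to follow-up. Step 2 would then remove it from Week 96, although day 660 lies in (631, 687].
4. State that off-drug make-up or unscheduled values beyond day 351 or 687 stay out.

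Subjects whose last dose plus one day is on or before day 351 or 687 keep the present upper bound. The cost is an SAP amendment and a small programming change. The downside is that a few Week 48 or Week 96 values will be more than 14 days past target, which every other window from Week 12 on already allows.

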### 9.8.1 Liver Function Tests

The central laboratory will notify the medical monitor of alanine transaminase (ALT) or aspartate transaminase (AST)  $>3 \times$  upper limit of normal (ULN) and total bilirubin  $>2 \times$  ULN that are derived from centrally submitted samples.

Subjects with new treatment-emergent (TE) ALT or AST elevations of  $>3 \times$  ULN, with or without total bilirubin  $>2 \times$  ULN, must be followed closely, including confirmatory testing performed by the central laboratory within 48 to 72 hours of the initial finding and subsequent close monitoring of ALT, AST, and bilirubin levels, as clinically indicated.

If a subject cannot return to the site for confirmatory testing, a local laboratory may be used. Local laboratory results must be reported immediately to the medical monitor, and the subject must have the tests repeated and sent to the central laboratory as soon as possible (ideally within 48 to 72 hours).

Study drug administration **must be interrupted** immediately (prior to confirmatory testing) if any of the following criteria are met:

- ALT or AST  $>8 \times$  ULN
- ALT or AST  $>5 \times$  ULN for more than 2 weeks
- ALT or AST  $>3 \times$  ULN, in association with total bilirubin  $>2 \times$  ULN and/or clinical jaundice

A thorough investigation of potential causes should be conducted, and the subject should be followed closely for clinical progression.

Subjects who enroll in this study on a drug interruption because of transaminase elevations in a parent study may NOT receive the first dose of study drug until transaminases return to baseline values or  $\leq 2 \times$  ULN, whichever is higher.

Study drug administration **must be discontinued** if the following criterion is met:

- Subsequent ALT or AST values confirm the initial elevation that satisfied the interruption rule (above), and no convincing alternative etiology (e.g., acetaminophen use, viral hepatitis, alcohol ingestion) is identified, regardless of whether transaminase levels have improved.

All subjects in whom treatment is discontinued for elevated transaminases (and bilirubin, as applicable) should have these levels monitored closely until levels normalize or return to baseline.

If an alternative, reversible cause of transaminase elevation with or without increased bilirubin or clinical jaundice has been identified, subjects may receive study drug once transaminases return

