### **11.2.6 Electrocardiograms**

Standard 12-lead ECGs will be performed using a machine with printout. Additional standard 12-lead ECGs will be performed at any other time if clinically indicated.

Subjects will be instructed to rest for at least 5 minutes before having an ECG performed.

The ECG traces will be manually read at the study site. A printout of the ECG traces will be made for safety review by the investigator and maintained with source documentation. Clinically significant ECG abnormalities occurring during the study through completion of study participation will be recorded as AEs.

To ensure the safety of the subjects, a qualified individual at the study site will make comparisons to baseline measurements. If the QTcF is increased by >60 msec from the baseline or an absolute QTcF value is  $\geq 500$  msec for any scheduled ECG, 2 additional ECGs will be performed approximately 2 to 4 minutes apart to confirm the original measurement. If either of the QTcF values from these repeated ECGs remains above the threshold value (>60 msec from baseline or  $\geq 500$  msec), a single ECG will be repeated at least hourly until QTcF values from 2 successive ECGs fall below the threshold value that triggered the repeat measurement. Further details pertaining to ECGs will be provided to sites in the ECG Manual.

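### The SAP's by-visit rules let outcome-triggered repeats replace a scheduled ALT/AST value or be averaged into QTcF, pulling those by-visit summaries modestly toward normal

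*SAP*

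**What the plan says.** SAP 12.1, Table 12-1 footnote 2, sets the scope: "The analysis visit windows will be applied using the following rules for both scheduled and unscheduled visits". Within a window, "The measurement closest to the target day will be used". Then: "If there are multiple measurements with the same closest distance from the target day, the latest measurement will be used". Same-day values have their own ranking: "For multiple measurements on the same day, unscheduled measurements will be treated as later than scheduled measurement". Nothing gives the scheduled measurement priority.

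ECGs are handled separately in SAP 12.1, Derived Variables 4. When several are recorded on one calendar day, "For summary purpose, the average value will be used as the ECG on that day". The threshold analysis uses every ECG value.

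The protocol says when repeats are required:

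- Section 9.8.1: a new treatment-emergent ALT or AST above 3×ULN needs "confirmatory testing performed by the central laboratory within 48 to 72 hours of the initial finding". If an interruption criterion is met, study drug stops before that confirmatory test.
- Section 11.2.6: a scheduled QTcF more than 60 msec above baseline, or at least 500 msec, leads to 2 further ECGs. If either remains above the threshold, "a single ECG will be repeated at least hourly until QTcF values from 2 successive ECGs fall below the threshold value" that triggered the repeats.

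**The concern.** A by-visit summary describes one value per subject at a planned time. If each subject contributes the scheduled value, chance highs and chance lows cancel across subjects. These rules break that symmetry, because the protocol-mandated confirmatory repeats follow high results only. A high ALT/AST can be replaced by its retest, and a high QTcF is averaged with recordings that may continue until they fall. Regression to the mean then works mostly in one direction. For ALT/AST, a sample taken after interruption can also stand in for the on-drug sample that caused the interruption, in a table meant to show change on treatment.

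Safety is the study's only objective, laboratory values and ECGs are named in the primary endpoint, and the analysis is descriptive (SAP 6.1 and 9.1.3). The by-visit tables are therefore part of the result itself.

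**Working it through.** The documents give no power, SD or expected event rate, and about 158 is only an expected enrolment. There is no plan figure to reproduce. The displacement counts follow from the SAP rule once visit timing is assumed. Everything on size rests on assumed inputs, shown as ranges.

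**1. How often an ALT/AST retest displaces the scheduled value**

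Inputs: visit window ±5 days, or ±3 days for Day 15 (Protocol Table 3-1); retest 48 to 72 hours after the finding (Protocol 9.8.1), taken here as 2 or 3 days after the scheduled sample; SAP rule of closest to target, ties to the latest. Assumption: the scheduled visit is equally likely on each day of its window.

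Let s be the scheduled day minus the target day and k the days to the retest. The retest is used if |s + k| ≤ |s|, that is, if s ≤ −k/2.

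| k (days) | Offsets s displaced | ±5-day visits | Day 15 (±3 days) |
|---|---|---|---|
| 2 | −5 to −1 | 5/11 = 45% | 3/7 |
| 3 | −5 to −2 | 4/11 = 36% | 2/7 |
| 4 | −5 to −2 | 4/11 = 36% | – |
| 5 | −5 to −3 | 3/11 = 27% | – |

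A scheduled sample taken on or after the target day is never displaced by a later-day retest.

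**2. What displacement does to an ALT/AST visit summary**

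Illustration (assumed): 150 subjects, 3 of them at 6×ULN, each retested at 4×ULN.

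- Mean: 3 × (4/11 to 5/11) × 2×ULN / 150 = 0.015 to 0.018×ULN lower.
- Maximum: if all three share it, it falls only when all three are displaced: (4/11)³ = 5% to (5/11)³ = 9%. If one subject alone holds it, 36% to 45%.
- SD: SD² = [146·b² + 147·(m − M)² + Σ(v − M)²]/149, where b and m are the SD and mean of the other 147 subjects, v the three high values and M the overall mean. With m = 0.6×ULN and nobody displaced, SD = 0.815 for b = 0.3 and 1.097 for b = 0.8. Averaging over 0 to 3 displaced subjects, the expected SD runs from 0.708 (b = 0.3, k = 2) to 1.036 (b = 0.8, k = 3), a fall of 13.1% to 5.5%.

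A simulation at n = 158 used log-normal ALT (median 0.5 to 0.7×ULN; log-scale SD 0.5 to 0.7 between and 0.3 to 0.4 within subjects) and a retest at 0.7 to 1.0 times the subject's level. About 40% of results above 3×ULN were displaced. Four scenarios:

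| Mean shift (×ULN) | SE of visit mean | Ratio |
|---|---|---|
| −0.0005 | 0.030 | 0.02 |
| −0.0076 | 0.051 | 0.15 |
| −0.0104 | 0.051 | 0.20 |
| −0.0307 | 0.074 | 0.41 |

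The retest was higher than the first value in 6% to 14% of triggered cases, so the direction is expected but not certain.

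**3. QTcF**

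Example with assumed values: baseline 410 msec; scheduled ECG 475 (+65, trigger); confirmatory ECGs 472 (+62, still above) and 470 (+60); hourly ECGs 455 and 452, both below. The by-visit value is (475 + 472 + 470 + 455 + 452)/5 = 464.8, a change of +54.8 msec against +65 for the scheduled ECG. The threshold table still counts the increase above 60 msec.

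Simulation of the full 11.2.6 sequence, n = 158, assumed mean change 0 or 5 msec:

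| SD of single-ECG change (msec) | Expected triggers per visit | Shift in a triggered subject (msec) | Shift in visit mean (msec) | SE (msec) | Ratio |
|---|---|---|---|---|---|
| 17.3 | 0.05 | −14.4 | −0.005 | 1.38 | <0.01 |
| 22.7 | 0.7 | −14.2 | −0.06 | 1.80 | 0.03 |
| 26.0 | 2.8 | −16.5 | −0.29 | 2.07 | 0.14 |
| 29.2 | 4.8 | −14.2 | −0.43 | 2.32 | 0.19 |

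**The case against.** Much can be said for leaving the text alone, and several stronger readings fail.

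- A reader might infer from the same-day sentence that confirmatory repeats always replace the scheduled result. No repeat that the protocol prescribes falls under it: ALT/AST confirmation comes 48 to 72 hours later, and same-day ECGs are averaged. The ALT/AST route is the ordinary closest-to-target rule, which keeps the scheduled value in 6/11 to 7/11 of cases. The 48 to 72 hours also run from the finding; a longer gap from the blood draw lowers displacement (27% at 5 days).
- A reader might extend the bias to blood pressure or CK. Protocol 9.8.1 covers ALT, AST and bilirubin, and 11.2.3 asks only for consistent methodology in repeat vital signs. No abnormal-value trigger is stated for either.
- A reader might conclude that normal values are never retested. After resumption, transaminases and bilirubin are assessed weekly for 4 weeks whatever the result (9.8.1), extra tests are allowed when clinically appropriate (11.2.2), and COVID-19 make-up visits are permitted (Addendum 3.0). These can move a visit value either way.
- A reader might expect the by-visit maximum to contradict a threshold table at the same visit. Threshold tables are not by visit; they count subjects with at least one event in the treatment-emergent period.
- The triggering ECG stays in the average. In the simulation, the averaged value still lay 3 to 6 msec above the subject's true level, so for that subject it is closer to the truth than the single ECG. The distortion arises across subjects, because only high values are remeasured.
- Baseline may also be an unscheduled value, which may partly offset the change.

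All of this stands and limits the point. It does not remove it: a stated rule still selects or dilutes by-visit values according to the outcome.

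**Conclusion.** The point holds for by-visit ALT/AST and QTcF summaries only, as a low-cost improvement. The expected direction is toward normal. The shift in visit means is small: at most 0.41 SE for ALT and 0.19 SE for QTcF over the assumed ranges. The larger effects are on individual visit values (about 14 to 17 msec in a triggered QTcF subject), on the SD, and sometimes on the maximum. An off-drug ALT/AST value can represent an on-drug visit.

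This rests on evenly spread visit timing, a retest 2 to 3 days after the scheduled sample, and assumed variances. Detection of outliers is preserved: threshold tables cover the whole treatment-emergent period, the laboratory listing includes unscheduled results, clinically significant abnormalities are reported as AEs, and elevated transaminases are an event of special interest. The documents do not support a claim that safety signals would be missed.

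**What to change.** Three edits to SAP 12.1 and the threshold text:

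1. Footnote 2, rule 2: if the window contains a scheduled measurement, use the scheduled one closest to the target day. Use an unscheduled one, including a COVID-19 make-up visit, only when there is no scheduled measurement.
2. Derived Variables 4: base the by-visit ECG summary on the recording or recordings scheduled for that visit, and exclude repeats triggered under Protocol 11.2.6.
3. State that all values, scheduled and unscheduled, enter the laboratory and vital-sign threshold analyses. The SAP says this outright only for ECGs; for the other two it is implied by counting at least one event.

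The cost is a few SAP sentences and the matching programming, with no new data and no change to study conduct. The downside is that a technically faulty scheduled value stays in the by-visit table unless it is queried and corrected in the database.
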